SOC 2 [4][5]	xx x (xx%)	xx x (xx%)	xx x (xx%)	xx x (xx%)	xx x (xx%)	xx x (xx%)	xx x (xx%)	xx x (xx%)	xx x (xx%)	xx x (xx%)	xx x (xx%)	xx x (xx%)
Preferred Term 1	xx x (xx%)	xx x (xx%)	xx x (xx%)	xx x (xx%)	xx x (xx%)	xx x (xx%)	xx x (xx%)	xx x (xx%)	xx x (xx%)	xx x (xx%)	xx x (xx%)	xx x (xx%)
Preferred Term 2	xx x (xx%)	xx x (xx%)	xx x (xx%)	xx x (xx%)	xx x (xx%)	xx x (xx%)	xx x (xx%)	xx x (xx%)	xx x (xx%)	xx x (xx%)	xx x (xx%)	xx x (xx%)
Preferred Term 3	xx x (xx%)	xx x (xx%)	xx x (xx%)	xx x (xx%)	xx x (xx%)	xx x (xx%)	xx x (xx%)	xx x (xx%)	xx x (xx%)	xx x (xx%)	xx x (xx%)	xx x (xx%)
Preferred Term 4	xx x (xx%)	xx x (xx%)	xx x (xx%)	xx x (xx%)	xx x (xx%)	xx x (xx%)	xx x (xx%)	xx x (xx%)	xx x (xx%)	xx x (xx%)	xx x (xx%)	xx x (xx%)

Continue ...

Abbreviations: AE, adverse event; COL, Control to Open Label; SOC, system organ class; TOL, Treatment to Open Label

Note: AEs coded using the MedDRA dictionary Version 21.0 or later. Given in the table are subject counts and percentages. At each level of summation, subjects are counted only once. Subjects experiencing AEs of more than one severity are summarized according to the maximum severity experienced over all episodes of an AE.

- [1] Treatment to Open Label (TOL): The TOL population comprises treatment subjects from ITT population who received active stimulation through Week 12, completed Week 12 assessments, continued to receive active stimulation during open-label follow-up, and for whom follow-up data are available.
- [2] Control to Open Label (COL): The COL population comprises control subjects from ITT population who received non-active (sham) stimulation through Week 12, switched to active stimulation after completing Week 12 assessments, continued to receive active stimulation during open-label follow-up, and for whom follow-up data are available.
- [3] Safety population comprises all enrolled subjects.
- [4] Percentage calculated based on each analysis population (i.e., TOL, CL, Safety).
- [5] AEs judged to be “Definitely related” or “Probably related” are reported as “Related”.

Reference: Listing 16.x.x.x

SOURCE: xxxxx SAS 9.4 {program location} {run date/time} }

Table 14.8.3.4
Implant Device-Related AEs by SOC and Maximum Severity: All Events

Repeat Table 14.8.3.3 for implant device-related adverse events

Table 14.8.3.5
Stimulation-Related AEs by SOC and Maximum Severity: All Events

Repeat Table 14.8.3.3 for stimulation-related adverse events

Table 14.8.3.6
Energizer-Related AEs by SOC and Maximum Severity: All Events

Repeat Table 14.8.3.3 for Energizer-related adverse events

Table 14.8.3.7
Explant Procedure-Related Adverse Events by SOC and Maximum Severity: All Events

Repeat Table 14.8.3.3 for explant procedure-related adverse events

Table 14.8.3.8
 Device Deficiency

Variable	TOL [1] (N=xxx)		COL [2] (N=xxx)		Safety Population [3] (N=xxx)	
	Events	n (%)	Events	n (%)	Events	n (%)
Any study device deficiency [4]	xx	xx (xx.x%)	xx	xx (xx.x%)	xx	xx (xx.x%)
Relationship of study device deficiency [4]	xx	xx (xx.x%)	xx	xx (xx.x%)	xx	xx (xx.x%)
MicroRegulator (Implant)	xx	xx (xx.x%)	xx	xx (xx.x%)	xx	xx (xx.x%)
POD	xx	xx (xx.x%)	xx	xx (xx.x%)	xx	xx (xx.x%)
Energizer	xx	xx (xx.x%)	xx	xx (xx.x%)	xx	xx (xx.x%)
Stimulation	xx	xx (xx.x%)	xx	xx (xx.x%)	xx	xx (xx.x%)
Prescription Pad	xx	xx (xx.x%)	xx	xx (xx.x%)	xx	xx (xx.x%)
IFU/Labeling	xx	xx (xx.x%)	xx	xx (xx.x%)	xx	xx (xx.x%)
Study device deficiency associated with AE [4]	xx	xx (xx.x%)	xx	xx (xx.x%)	xx	xx (xx.x%)
Study device deficiency associated with SAE [4]	xx	xx (xx.x%)	xx	xx (xx.x%)	xx	xx (xx.x%)

Abbreviations: AE, adverse event; COL, Control to Open Label; POD, Positioning Orientation Device; SAE, serious adverse event; SOC, system organ class; TOL, Treatment to Open Label

Note: Given in the table are subject counts and percentages. At each level of summation, subjects are counted only once. Subject experiencing several episodes of the same type of study device deficiency is counted once.

- [1] Treatment to Open Label (TOL): The TOL population comprises treatment subjects from ITT population who received active stimulation through Week 12, completed Week 12 assessments, continued to receive active stimulation during open-label follow-up, and for whom follow-up data are available.
- [2] Control to Open Label (COL): The COL population comprises control subjects from ITT population who received non-active (sham) stimulation through Week 12, switched to active stimulation after completing Week 12 assessments, continued to receive active stimulation during open-label follow-up, and for whom follow-up data are available.
- [3] Safety population comprises all enrolled subjects.
- [4] Percentage calculated based on each analysis population (i.e., TOL, CL, Safety).

Reference: Listing 16.x.x.x

SOURCE: xxxxx SAS 9.4 {program location} {run date/time}

Table 14.8.3.9
Protocol Deviations

Variable	OL PTE [1] (N=xxx)		CO PTE [2] (N=xxx)		Safety Population [3] (N=xxx)	
	Events	n (%)	Events	n (%)	Events	n (%)
Any protocol deviation [4]	xx	xx (xx.x%)	xx	xx (xx.x%)	xx	xx (xx.x%)
Minor protocol deviations [4]						
Improper documentation of consent	xx	xx (xx.x%)	xx	xx (xx.x%)	xx	xx (xx.x%)
Visit or assessment not done	xx	xx (xx.x%)	xx	xx (xx.x%)	xx	xx (xx.x%)
Visit or assessment completed out of window	xx	xx (xx.x%)	xx	xx (xx.x%)	xx	xx (xx.x%)
AE not reported within required schedule	xx	xx (xx.x%)	xx	xx (xx.x%)	xx	xx (xx.x%)
Received medication not allowed per protocol	xx	xx (xx.x%)	xx	xx (xx.x%)	xx	xx (xx.x%)
Subject or study staff unblinded	xx	xx (xx.x%)	xx	xx (xx.x%)	xx	xx (xx.x%)
Other, specify	xx	xx (xx.x%)	xx	xx (xx.x%)	xx	xx (xx.x%)
Protocol deviations due to COVID-19 [4]						
Visit or assessment not done	xx	xx (xx.x%)	xx	xx (xx.x%)	xx	xx (xx.x%)
Visit or assessment completed out of window	xx	xx (xx.x%)	xx	xx (xx.x%)	xx	xx (xx.x%)
Visit or assessment completed not per protocol	xx	xx (xx.x%)	xx	xx (xx.x%)	xx	xx (xx.x%)
Protocol deviations associated with AE [4]	xx	xx (xx.x%)	xx	xx (xx.x%)	xx	xx (xx.x%)
Protocol deviations associated with SAE [4]	xx	xx (xx.x%)	xx	xx (xx.x%)	xx	xx (xx.x%)

Abbreviations: AE, adverse event; COL, Control to Open Label; SAE, serious adverse event; TOL, Treatment to Open Label

Note: Given in the table are subject counts and percentages. At each level of summation, subjects are counted only once.

- [1] Treatment to Open Label (TOL): The TOL population comprises treatment subjects from ITT population who received active stimulation through Week 12, completed Week 12 assessments, continued to receive active stimulation during open-label follow-up, and for whom follow-up data are available.
- [2] Control to Open Label (COL): The COL population comprises control subjects from ITT population who received non-active (sham) stimulation through Week 12, switched to active stimulation after completing Week 12 assessments, continued to receive active stimulation during open-label follow-up, and for whom follow-up data are available.
- [3] Safety population comprises all enrolled subjects.
- [4] Percentage calculated based on each analysis population (i.e., TOL, CL, Safety).

Reference: Listing 16.x.x.x

Variable	OL PTE [1] (N=xxx) Events n (%)	CO PTE [2] (N=xxx) Events n (%)	Safety Population [3] (N=xxx) Events n (%)
SOURCE: xxxxx SAS 9.4 {program location}	{run date/time}}		

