Baseline	Information and values collected during Screening. The RA disease activity assessments that serve as the baseline assessments used for determination of the primary and key secondary efficacy endpoints must be performed on the day of informed consent.
CDAI	
The CDAI score is based on 4 items:
 
 • TJC28 • SJC28

Term	Definition
	
 SGA EGA 
The CDAI score is calculated as follows and ranges from 0 to 76:
 
 CDAI = TJC28 + SJC28 + SGA + EGA 
The CDAI score corresponds to the current RA activity:
 
 0 to \leq 2.8 Remission >2.8 to \leq 10 Low disease activity (LDA) >10 to \leq 22 Moderate disease activity > 22 High disease activity 
The MCID is a score reduction by 12 if starting in high activity, 6 if starting in moderate activity, and 1 if starting in low activity.

Control to Open Label (COL) population	Control subjects from ITT population who received non-active (sham) stimulation through Week 12, switched to active stimulation after completing Week 12 assessments, continued to receive active stimulation during open-label follow-up, and for whom follow-up data are available.
Crossover	The process of switching from an initially assigned treatment to the other treatment being studied.
DAS28-CRP	
The DAS28-CRP score is a composite index providing a measure of disease activity, comprising:
 
 TJC28 SJC28 SGA hsCRP (mg/L) 
A total score ranges from 0 to 10 and is computed as follows:
 $\text{DAS28-CRP} = 0.56 * \text{sqrt}(\text{TJC28}) + 0.28 * \text{sqrt}(\text{SJC28}) + 0.36 * \ln(\text{CRP}+1) + 0.014 * \text{SGA} + 0.96$ 
The DAS28-CRP score corresponds to the current RA activity:
 
 0 to $<$ 2.6 Remission 2.6 to $<$ 3.2 LDA 3.2 to \leq 5.1 Moderate activity > 5.1 High activity 
A DAS28-CRP score reduction by 1.2 represents the MCID.

Day 0 (randomization, initiation of stimulation)	
Scheduled study visit occurring 14 to 21 days after Implant Procedure during which subjects undergo the following study procedures in the order specified:
 
 Day 0 assessments Randomization Initiation of stimulation 
Subjects must receive final surgical clearance with an approval to initiate study treatment before proceeding to the Day 0 visit.

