8 STUDY OBJECTIVE AND ENDPOINTS

The overall objective of this study is to assess the safety and efficacy of the SetPoint System for the treatment of adult patients with active, moderate to severe RA who have had an inadequate response or intolerance to biologic or targeted synthetic DMARDs.

The study specific objectives and endpoints are defined in **Table 3**.

Table 3: Study Objectives and Endpoints

Objective	Endpoint	Justification of Endpoint
Primary		
To assess the efficacy of the SetPoint System	ACR20 response at Week 12 from baseline on the day of informed consent	The ACR20 response is the most commonly used, RA-specific, clinically relevant, valid and reliable measure of therapeutic effect and clinical benefit of the investigational treatment on signs, symptoms and physical functions.
Secondary		
To further assess the efficacy of the SetPoint System in terms of clinically meaningful benefits	
Key secondary efficacy endpoints adjusted for multiplicity:
 
 • ACR20 response at Week 12 from Day 0 • DAS28-CRP good/moderate EULAR response at Week 12 • DAS28-CRP response (MCID -1.2) at Week 12 • HAQ-DI response (MCID -0.22) at Week 12 	These are RA-specific, clinically relevant, valid and reliable measures of therapeutic effect of the investigational treatment on signs, symptoms and physical functions.
Exploratory		
To provide further information on the therapeutic effect of the SetPoint System	
 • Exploratory endpoints include, but are not limited to: • ACR20 response at Week 24, 48, 96, 144 and 192 • ACR50/70 response at Week 12, 24, 48, 96, 144 and 192 • 20/50/70 response for ACR components (TJC28, SJC28, Subject Pain, SGA, HAQ-DI, EGA, hsCRP) based on change from baseline to Week 12, 24, 48, 96, 144 and 192 • DAS28-CRP score change from baseline, LDA/remission at Week 12, 24, 48, 96, 144 and 192 • DAS28-CRP response (MCID, good/moderate EULAR) at Week 24, 48, 96, 144 and 192 • CDAI score change from baseline, LDA/remission, response (MCID) at Week 12, 24, 48, 95, 144 and 192 • EQ-5D-5L score change from baseline, response at Week 12, 24, 48, 96, 144 and 192 • SF-36/PCS/MCS score change from 	These are clinically relevant, and validated measures of the therapeutic effect on composite measures, patient-reported outcomes, inflammatory biomarkers and structural progression of disease.

CONFIDENTIAL

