4.2 Exploratory Analysis

During the open-label follow-up, changes in exploratory efficacy endpoints at Week 24, 48, 96, 144 and 264 (end of study) will be evaluated in comparison to baseline and Day 0 for the treatment population and Week 12 for the crossover population using data for all subjects available at a given timepoint (**Table 2**). Refer to Section 5.2 for definitions of populations.

Table 2: Summary of Exploratory Efficacy Endpoints

Endpoint	Display	TOL	COL	Subgroup
ACR20/50/70 response	T, L	Y	Y	Y [1]
DAS28-CRP moderate/good EULAR response	T, L	Y	Y	Y
DAS28-CRP response (MCID)	T, L	Y	Y	Y
HAQ-DI score change and response (MCID)	T, L	Y	Y	Y
ACR components (TJC28, SJC28, Subject Pain, SGA, HAQ-DI, EGA, hsCRP) 20/50/70response	T, L	Y	Y	--
DAS28-CRP score change, LDA/remission	T, L	Y	Y	--
CDAI score change, LDA/remission, response (MCID)	T, L	Y	Y	--
RAMRIS (bone erosion, osteitis, synovitis, CARLOS) score change, progression (bone erosion) at Week 24	T, L	Y	Y	--
EQ-5D-5L score change	T, L	Y	Y	--
SF-36/PCS/MCS score change	T, L	Y	Y	--
Percent change in inflammatory biomarkers at Week 24	T, L	Y	Y	--
Subject satisfaction at Week 24	T, L	Y	Y	--

Abbreviations: ACR, American College of Rheumatology; CARLOS, cartilage loss score; CDAI, Clinical Disease Activity Index; COL, control to open label; CRP, C-reactive protein; DAS, Disease Activity Score; EGA, evaluator's global assessment; EQ-5d-5L, EuroQol 5 domains 5 levels; EULAR, European League Against Rheumatism; HAQ-DI, Health Assessment Questionnaire Disability Index; hsCRP, high sensitivity CRP; L, listings; LDA, low disease activity; RAMRIS, Rheumatoid Arthritis MRI Scoring System; SF-36, Short Form Survey with 36 items; SGA, subject's global assessment; T, tables; TJC, tender joint count; TOL, treatment to open label; SJC, swollen joint count; Y, yes.

[1] Subgroup analyses as defined in Section 6.3

Note: All score values are determined at all timepoints, unless stated otherwise. All response rates are determined based on change from baseline (i.e., on the day of informed consent for OL PTE population and Week 12 for CO PTE population) to a specified timepoint. Refer to Section 5.2 for definitions of populations Sections 6.2 for definition of response for specific endpoints.

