6 EXPLORATORY EFFICACY ANALYSES

6.1 General Considerations

For each follow-up time point, all dichotomous variables will be reported as responders / patients who have achieved that follow-up duration, percentage of responders, and 95% CI.

Values will be reported at each follow-up timepoint.

For continuous measures, mean, SD, median, minimum and maximum will be presented at each time point.

Time will be measured from initiation of stimulation. Therefore study participants originally randomized to stimulation will, for example, have Week 24 visits represented at 24 weeks of follow-up while study participants randomized to sham will have Week 24 visits represented as 12 weeks, since they will have been on stimulation on for 12 weeks at the Week 24 visit.

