6.2.1 ACR20/50/70

A subject achieves ACR20/50/70 response when this subject experiences a $\geq 20\%/50\%/70\%$, respectively improvement from baseline to a given timepoint in TJC28, SJC28, and at least 3 of the following 5 items:

- Subject's pain assessment
- SGA
- EGA
- HAQ-DI
- hsCRP

For all visits, if any of the component scores are missing, then those scores will be considered as not having met the criteria for improvement. If 3 or more of the 5 remaining ACR measures are missing, ACR20/50/70 will each be considered missing.

For component scores with missing baseline values or a baseline value of 0, the percentage improvement cannot be calculated, and the component will be considered as not having met the criteria for improvement for all visits.

20/50/70 response for each component (TJC28, SJC28, Subject's Pain Assessment, SGA, HAQ-DI, EGA, hsCRP) corresponds to 20, 50 and 70% improvement from baseline to a given timepoint, respectively.

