ACR50 response from baseline [4]		
Week 24		
N	xx	xx
Yes [3]	xx (xx.x%)	xx (xx.x%)
95% CI	(xx.x, xx.x)	(xx.x, xx.x)
Repeat for:		
Week 36		
Week 48		
Week 60		
Week 72		
Week 84		
Week 96		
Week 108		
Week 120		
Week 132		
Week 144		
Week 156		
Week 168		
Week 180		
Week 192		
ACR50 response from initiation of stimulation [5]		
Week 24		
N	xx	xx
Yes [3]	xx (xx.x%)	xx (xx.x%)
95% CI	(xx.x, xx.x)	(xx.x, xx.x)

Variable	TOL [1] (N=xxx)	COL [2] (N=xxx)
Repeat for:		
Week 36		
Week 48		
Week 60		
Week 72		
Week 84		
Week 96		
Week 108		
Week 120		
Week 132		
Week 144		
Week 156		
Week 168		
Week 180		
Week 192		
ACR70 Response from baseline [4]		
Week 24		
N	xx	xx
Yes [3]	xx (xx.x%)	xx (xx.x%)
95% CI	(xx.x, xx.x)	(xx.x, xx.x)
Repeat for:		
Week 36		
Week 48		
Week 60		
Week 72		
Week 84		
Week 96		
Week 108		
Week 120		
Week 132		
Week 144		
Week 156		
Week 168		
Week 180		

Variable	TOL [1] (N=xxx)	COL [2] (N=xxx)
Week 192		
ACR70 response from initiation of stimulation [5]		
Week 24		
N	xx	xx
Yes [3]	xx (xx.x%)	xx (xx.x%)
95% CI	(xx.x, xx.x)	(xx.x, xx.x)
Repeat for:		
Week 36		
Week 48		
Week 60		
Week 72		
Week 84		
Week 96		
Week 108		
Week 120		
Week 132		
Week 144		
Week 156		
Week 168		
Week 180		
Week 192		

Abbreviations: ACR, American College of Rheumatology; CI, confidence interval; COL, Control to Open Label; TOL, Treatment to Open Label

- [1] Treatment to Open Label (TOL): The TOL population comprises treatment subjects from ITT population who received active stimulation through Week 12, completed Week 12 assessments, continued to receive active stimulation during open-label follow-up, and for whom follow-up data are available.
- [2] Control to Open Label (COL): The COL population comprises control subjects from ITT population who received non-active (sham) stimulation through Week 12, switched to active stimulation after completing Week 12 assessments, continued to receive active stimulation during open-label follow-up, and for whom follow-up data are available.
- [3] Percentage calculated based on each analysis population (i.e., TOL, COL)
- [4] Baseline on the day of informed consent for TOL and Week 12 for COL
- [5] Initiation of stimulation at Day 0 for TOL and Week 12 for COL

Reference: Listing 16.x.x.x

SOURCE: xxxxx SAS 9.4 {program location} {run date/time} }

Table 14.8.2.1.1
 Subgroup Analysis of ACR20 Response: Prior b/tsDMARDs

Variable	TOL [1] (N=xxx)	COL [2] (N=xxx)
ACR20 response from baseline [4]		
Prior b/tsDMARD < 4		
Week 24		

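### In the long-term SAP, both response references for crossover subjects are Week 12, so paired rows repeat, none uses the protocol baseline, and a zero joint count at Week 12 rules out ACR response

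*SAP*

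**What the plan says.** **Long-term SAP (CLP-008)**

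- Section 4.2 refers the crossover population to Week 12. The note to Table 2 repeats this for response rates, with baseline "on the day of informed consent for OL PTE population and Week 12 for CO PTE population". OL PTE and CO PTE are the former names of TOL and COL.
- Appendix B, Table 14.8.2.1, footnote [4], for the from-baseline rows: "Baseline on the day of informed consent for TOL and Week 12 for COL".
- The same table, footnote [5], for the from-initiation rows: "Initiation of stimulation at Day 0 for TOL and Week 12 for COL". Both footnotes recur through the response and score tables.
- Section 6.1: "Time will be measured from initiation of stimulation". By its own example, a COL Week 24 visit is to be shown as 12 weeks.
- Section 6.2.1 defines ACR response as "improvement from baseline to a given timepoint in TJC28, SJC28, and at least 3 of the following 5 items". It adds: "For component scores with missing baseline values or a baseline value of 0, the percentage improvement cannot be calculated". Such a component counts as not improved at all visits.

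**Protocol**

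- Section 3 defines Baseline as "Information and values collected during Screening", with no exception for crossover subjects.
- Section 8, Table 3, lists the ACR component responses "based on change from baseline to Week 12, 24, 48, 96, 144 and 192". That is one baseline, earlier than Week 12, used for all visits.
- Section 10.1 requires at least 4 tender and 4 swollen joints for entry.

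**The concern.** Two row sets with different names should answer two different questions. The SAP treats them as distinct: for the subgroup by RA severity at initiation of stimulation, it tells programmers to drop the from-baseline part of the tables. For TOL they do differ, since consent day is not Day 0. For COL they cannot.

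Two things are at stake. First, the protocol's exploratory endpoint, change from the Screening baseline at Week 24 and later, is never produced for the control arm. Secondly, Week 12 is a post-treatment visit at which a joint count may be 0, and section 6.2.1 turns a zero reference count into non-response at every later visit. TOL has one row protected from this by the entry criteria. COL has none.

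**Working it through.** The plan states no figure on this point, so there is none to reproduce. The check sets the definitions side by side and then applies the ACR rule.

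**1. Reference visit by row**

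| Row | TOL | COL |
|---|---|---|
| From baseline (footnote [4]) | Consent day | Week 12 |
| From initiation (footnote [5]) | Day 0 | Week 12 |
| Protocol baseline (section 3) | Screening | Screening |

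For COL the subjects, visits and reference are the same in both rows, so the entries are equal by construction. Neither matches the protocol baseline.

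**2. The zero-count rule**

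Response at threshold *t* requires (reference − visit)/reference ≥ *t* for TJC28, for SJC28 and for at least 3 of the other 5 items. A reference of 0 fails that item. Because both joint counts are mandatory, a zero in either one rules out response whatever happens later.

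An invented COL subject shows the effect:

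| Item | Consent | Week 12 | Week 24 | Change vs Week 12 | Change vs consent |
|---|---|---|---|---|---|
| TJC28 | 12 | 3 | 0 | 100% | 100% |
| SJC28 | 10 | 0 | 0 | not computable, so failed | 100% |
| Pain | 7 | 4 | 1 | 75% | 86% |
| SGA | 7 | 4 | 1 | 75% | 86% |
| EGA | 6 | 2 | 0 | 100% | 100% |
| HAQ-DI | 1.5 | 1.0 | 0.25 | 75% | 83% |
| hsCRP | 12 | 8 | 2 | 75% | 83% |

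Against consent this subject is an ACR20, ACR50 and ACR70 responder. Against Week 12 the subject is a non-responder at all three levels, solely because SJC28 was already 0. Coding the rule and running it on 200,000 random reference/visit pairs gave 34,843 pairs with a zero joint count at reference and no ACR20 responder among them.

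With a consent-day reference neither joint count can be 0, because entry requires at least 4 of each.

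**3. Which outputs are reached**

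The zero rule affects ACR20/50/70 and the 20/50/70% response row of the component that is 0. EULAR response and the DAS28-CRP, HAQ-DI and CDAI MCID responses use absolute change, so the rule does not reach them, although their paired COL rows still repeat. Low disease activity and remission need no reference visit.

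**4. Size**

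The share of controls with a zero joint count at Week 12 is not in the documents, so it is assumed. The planned control arm is 125 (Protocol 17.2). COL can be smaller, because it requires continued active stimulation and available follow-up data.

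| Assumed share | Subjects (share × 125) | Highest attainable ACR rate (1 − share) |
|---|---|---|
| 2% | 2.5 | 98% |
| 5% | 6.25 | 95% |
| 10% | 12.5 | 90% |
| 15% | 18.75 | 85% |
| 20% | 25 | 80% |

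The shells tabulate Week 24 to Week 192 every 12 weeks: (192 − 24)/12 + 1 = 15 visits.

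**The case against.** The strongest reply is that Week 12 is a deliberate choice. Section 4.2 states it and section 6.1 measures time from initiation, so the COL result answers a coherent question: change since active stimulation began. A consent-day reference mixes in change during the sham period. The protocol sentence fixing the consent-day baseline concerns the primary and key secondary endpoints, and Protocol section 17 leaves the open-label analysis to its own SAP.

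This stands as a defence of the from-initiation row. It does not explain why the from-baseline row should give the same answer again, or why the protocol's single baseline running through Week 12 to Week 192 has no COL result. Both questions can be answered, because there are already two rows.

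A reader might infer more than the documents support:

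- **That the Week 12 reference is a slip.** Section 4.2 shows that it is intended. The defect is using it under both labels.
- **That COL subjects in sustained remission disappear from the results.** They appear in the DAS28-CRP and CDAI low-disease-activity and remission rows.
- **That they are counted as failures at every scheduled visit.** Section 5.5 sets missed visits to missing, and the shells tabulate 15 visits, not the 21 follow-up assessment visits of section 3.3.
- **That a TOL-versus-COL comparison is biased.** None is planned. The shells have no difference or p-value row, and section 6.1 asks only for percentages and confidence intervals within each population.

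The zero-count problem is also not unique to COL. A TOL subject with a zero count at Day 0 meets it in the from-initiation row. The difference is that TOL keeps a protected consent-day row.

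**Conclusion.** The point holds in this form. Every paired COL row in CLP-008 is a duplicate, and no COL change or response is reported against the protocol baseline. Both conclusions follow from the definitions and need no assumption. The zero-count rule then makes a COL subject with TJC28 or SJC28 of 0 at Week 12 an ACR20/50/70 non-responder at each non-missing later visit in both rows, and a non-responder on the percentage row for that count.

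The number of subjects is an assumption: about 2 to 25 if 2% to 20% of at most 125 controls are affected. The outputs are exploratory and descriptive, and the primary and key secondary analyses are untouched. The change is still worth making, because it alters a reported result at little cost.

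**What to change.** In CLP-008:

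1. Set the from-baseline rows to the Screening (consent-day) baseline for both TOL and COL. Amend footnote [4] throughout, the text of section 4.2, the Table 2 note and the listing notes together, since changing the footnote alone would contradict section 4.2.
2. Add Screening rows to the COL listings. Those for CDAI, DAS28-CRP, HAQ-DI, RAMRIS and biomarkers now start at Week 12.
3. Keep Week 12 for COL in the from-initiation rows, and label these by weeks since initiation, as section 6.1 requires.
4. Add a from-initiation row for RAMRIS, which has none, so that its Week 12 reference is not lost. It can be filled for COL only, because the schedule has no hand MRI at Day 0.
5. State how a zero count at initiation (Day 0 for TOL, Week 12 for COL) is handled in the ACR and percentage-response rows. Step 1 does not resolve this for the from-initiation rows.

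The cost is some extra programming and additional table and listing rows. The Screening data are already scheduled, so nothing new has to be collected.
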